4.3.1 Providers

The research coordinator will be responsible for the consent of the clinical team staff for enrollment in this study. The consent process begins once the participant is interested in being interviewed for the study. At this time, the researcher will conduct a thorough review of the consent details, including study procedure, risks, confidentiality, etc., with the potential participant. It is assumed that working providers in the field will be mentally capable of participating in the study; therefore, no screening measures will be undergone to obtain eligibility. Researchers and investigators will be available to answer any questions the professionals have prior to consenting. The consent must be done in a face to face meeting or via video conferencing by the researcher and the clinician. If consent is done through video conference, a signed consent form will still be collected by the research coordinator.

4.4 Semi-Structured Interview Process

4.4.1 Patients

After obtaining informed consent, the research coordinator will set up a time to complete the questionnaire and a 30-minute semi-structured interview with the patient before discharge. Patients will be asked at the time of consent if they are willing to provide an email address for reminders and updates. After 30 days of remote monitoring, the research coordinator will contact patients via phone to complete the survey. In addition to completing the surveys, the first patient group (first 40 patients from each cohort) will need to complete a 30-minute semi-structured interview.

At the study endpoint, the research team will make three phone attempts to reach the patient on different days and times. In addition to phone reminders, an email reminder and survey link will be pushed out to the patient's email address via REDCap if the patient opts to do so at the time of consent. If unable to reach the patient, the patient will then be contacted by their provider to remind them of completing the survey and interview if applicable.

Before the interview starts, the researcher will remind the participant not to use their name during the interview as it will be recorded. These interviews will be transcribed and then de-identified by study staff. They will also be reminded that recording is required for participation.

4.4.2 Providers

Upon signing the consent forms, the research coordinator will complete a self-administered survey and interview with the clinical team staff. After completion of phase 3, the research coordinator will send out a questionnaire link to the clinical staff to complete within five business days. The research coordinator may set up an appointment with the clinical team to complete the questionnaire via phone if the survey is not sent back, or if the survey contains skipped or missing questions. Throughout, recurring questions from REDCap will be pushed to the provider's email address for them to complete within 72 hours. At the study endpoint, the research coordinator will set up appointments with the clinical staff for a 30-minute interview.

Before the interview starts, the researcher will remind the provider not to use their name during the interview as it will be recorded. These interviews will be transcribed and then de-identified by study staff. They will also be reminded that recording is required for participation.

4.5 Record keeping and transcripts

The interview recordings will be sent to a transcription service company with whom the research team has a strong working relationship. The transcription service company have a secure server for uploads of recordings and delete them after transcription is complete. If any patient's name is recorded on the transcripts, we will have the transcription service replace the name with an abbreviation instead. Transcripts will be scrubbed of PHI during transcription and will be given a study ID number. Quality control to make sure all PHI has been removed from each transcript will be conducted by the Research Coordinator prior to analysis. The final transcripts will be analyzed by the study team. The list that links the transcripts to the research participants will also be stored on the secure collaboration portal. The recordings will be deleted once they have been transcribed and analyzed. The key for the study ID numbers will be destroyed once the analysis is complete.

4.6 Retrospective Cohort Comparison

We will analyze and compare readmission metrics and care escalation process measures against a usual care retrospective control sample of patients. We will include patients who meet the same inclusion and exclusion criteria from 36 months prior to the start of the study to determine which process measures may be valuable in informing the design and deployment of remote monitoring of HF patients at scale in the future.

We are asking for a waiver for the retrospective cohort, as this contains minimal risk to the cohort. The data scientist and research coordinator will use EDW to look up and perform chart reviews for patients meeting the criteria for the retrospective cohort. All data will be de-identified and stored on the collaboration portal. Only the PI, data scientist, and research coordinator will have access to the data at NorthShore. Deidentified data will also be provided to Carnegie Mellon University to conduct the

predictive analytics sub aim as detailed in this protocol. This data will be deidentified when provided and a DUA will be requested for this work. All data will be destroyed upon completion of the study by the data scientist and by Carnegie Mellon University.

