2.2 Experimental Plan and Methods

The goal of the study is to reduce readmission rates for high risk medical and surgical patients. Phase 1 will involve 5 high risk CHF patients. The goal of phase 1 is to understand how physIQ's platform Pinpoint IQ with a cascading set of alerts including the wearable device alerts, patient reported metrics, CAPE navigator or monitoring nurse alerts can be developed and improved upon to reduce the incidence of 30 day readmission. Phase 2 is the configuration and testing period before phase 3.

Phase 1

Phase 1 will assess the thresholds, process, and workflows of this cascading alert system. We will be enrolling 5 patients for this study at NorthShore University Health System.

CHF patients will be identified by an Enterprise Data Warehouse query that will report patients who meet specific inclusion and exclusion criteria daily. These criteria include being in the top 20% of the CAPE 30-day readmission risk prediction model, on the CHF service list at Evanston hospital, a patient of HF team, speaks English and does not have an implantable cardiomems device. The EDW query will be created and maintained by the clinical analytics team. These queries will be forwarded to the study coordinator who, when a qualifying patient is identified, will discuss with the CHF attendings regarding whether the patient is appropriate for this study. Patients will be approached by the study coordinator who will perform informed consent. If the patient is agreeable the patient will receive a kit from physIQ

prior to discharge. A Vital patch will be placed on the patient prior to discharge and the patch will be connected via blue tooth to the physIQ mobile device and pinpointIQ application. The study coordinator will teach the patient how to apply and remove the patch and what to do if there are issues with the patch. The study coordinator will also teach the patient how to use the mobile device and the physIQ application. The application will ask for the dry/current weight of the patient and this will be filled in prior to discharge.

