4.2 Inclusion and Exclusion Criteria

4.2.1 Patients

We will recruit CHF patients

CHF Cohort

Inclusion Criteria:

- Patient is an inpatient at Evanston Hospital
- Patient is followed by the heart failure clinical team post-discharge
- Patient has a history of heart failure
- Patient received at least one dose of IV diuretic during index hospitalization
- Patient is monitored by monitoring nurse post-discharge
- Patient discharges with any home health service
- Symptoms corresponding to NYHA function class II-IV
- Patient has heart failure with reduced left ventricular ejection fraction (LVEF)<40%, or HF with mid-ranged ejection fraction (LVEF 40-50%), or HF with preserved ejection fraction (LVEF≥50%)
- Patient is in the top 50% risk of readmission across NorthShore University HealthSystem's CAPE 30-day readmission model
- Patient is at least 18 years of age
- Patient is fluent in English
- Patient agrees to protocol-required procedures

Exclusion Criteria:

- Patient has cognitive or physical limitations that, in the opinion of the investigator, limit the patient's ability to maintain patch/wrist device, phone

- Patient has allergy to hydrocolloid adhesives
- Patient has present skin damage preventing them from wearing a study device
- Patient has renal dysfunction requiring dialysis
- Pregnancy

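### Section 4.6 requires historical controls to meet identical eligibility criteria, but some criteria cannot be read from past charts and the protocol holds two unreconciled sets

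*Protocol*

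**What the plan says.** Section 4.6 plans to compare readmission metrics and care-escalation measures in enrolled patients with a retrospective usual-care sample. Its rule for that sample is: "We will include patients who meet the same inclusion and exclusion criteria from 36 months prior to the start of the study". Under a waiver, staff will "use EDW to look up and perform chart reviews for patients meeting the criteria for the retrospective cohort". The section gives its purpose as learning which process measures could guide later remote monitoring.

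The eligibility list in 4.2.1, headed for the CHF cohort and not limited to a phase, includes:
- "Patient agrees to protocol-required procedures";
- "Patient is in the top 50% risk of readmission" on the health system's CAPE model;
- follow-up by the monitoring nurse after discharge;
- an exclusion that begins "Patient has cognitive or physical limitations that, in the opinion of the investigator" and concerns the ability to manage the patch and phone.

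Section 2.2, under Phase 1 (5 patients), describes a daily data-warehouse query with different terms: "being in the top 20% of the CAPE 30-day readmission risk prediction model", and that the patient "does not have an implantable cardiomems device". The coordinator then asks the CHF attendings whether each patient is suitable. Section 4.2.1 has neither the 20% threshold nor the cardiomems exclusion, and no text reconciles the two lists.

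**The concern.** The instruction to use identical criteria fails in two ways.

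First, some criteria exist only for people who were approached. Past patients were never asked to agree to study procedures. No investigator judged whether they could handle the device, and no attending screened them for the study. The monitoring-nurse criterion may also have no clear meaning in earlier usual care. Chart review can approximate some of these but cannot supply agreement.

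Second, the instruction does not point to one list. The 4.2.1 list is its most natural referent. If enrolment runs through the top-20% query while controls are drawn on the top-50% rule, the two groups have different expected readmission before any monitoring starts.

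What is at stake is misreading. Section 2.2 states: "The goal of the study is to reduce readmission rates for high risk medical and surgical patients". Section 4.6 holds the only readmission comparison that the protocol describes. A difference in either direction could be taken as a device effect, or as its absence, when it reflects who was selected. A larger control sample would not remove this, and a confidence interval would not show it.

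**Working it through.** The protocol gives no sample-size, power or effect figure for this comparison, so there is none to reproduce. What follows asks how large the selection effects could be if the device did nothing.

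**Inputs from the protocol.** Readmission 15-30% (1.2); 20 patients planned (4.3.1); 5 patients in Phase 1 (2.2). Everything else below is an assumption.

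**1. Sampling error with 20 enrolled patients.** Treating the control rate as known, the half-width is 1.96 × √(p(1−p)/20). This is 15.6 points at p = 0.15 and 20.1 points at p = 0.30. Expected events are 20 × 0.15 = 3 to 20 × 0.30 = 6.

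**2. Band mismatch: enrolled from the top 20%, controls from the top 50%.** Assume a binormal score with AUC 0.60-0.70, and calibrate the top-50% risk to 0.15 or 0.30.
- Percentiles taken within the heart-failure population (40% of the top half lies in the top fifth), all 20 enrolled in the narrower band:
  - AUC 0.60: top-20% risk 0.179 and 0.347, an excess of 2.9 and 4.7 points;
  - AUC 0.70: top-20% risk 0.212 and 0.400, an excess of 6.2 and 10.0 points;
  - risk ratios 1.16-1.41.
- Only the 5 Phase 1 patients in the narrower band: multiply by 5/20, giving 0.7-2.5 points and risk ratios 1.04-1.10.
- System-wide percentiles, where more heart-failure patients would sit high on the scale: assume 72% of them are in the system top 20% and 90% in the top 50%, an overlap of 72/90 = 80%. The excess is then 1.2-3.9 points if all 20 are in the narrower band.

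A cruder check assumes 30% readmission in the top 20% and 15% in the next 30%. With 40% overlap the pooled risk is 0.4 × 30 + 0.6 × 15 = 21%, a gap of 9 points. With 80% overlap it is 0.8 × 30 + 0.2 × 15 = 27%, a gap of 3 points.

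**3. Consent selection.** Let f be the share who consent and r the decliners' risk relative to consenters. The ratio of enrolled to control risk with no device effect is 1/(f + (1−f)r).
- f = 0.3, r = 1.5: 1/1.35 = 0.741, a shortfall of 3.9 points at 15% risk and 7.8 at 30%.
- f = 0.7, r = 1.1: 1/1.03 = 0.971, a shortfall of 0.4 and 0.9 points.
- Wider inputs, f = 0.2 and r = 2.0: 1/1.8 = 0.556, a shortfall of 6.7 and 13.3 points.
- If decliners were instead at lower risk, say f = 0.3 and r = 0.8: 1/0.86 = 1.163, an excess of 2.4 and 4.9 points.

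**4. Chance of an apparent drop of at least 10 points with no device effect.**
- At 15% risk: P(X ≤ 1 of 20) = 0.176 without selection, and 0.332 at risk 0.111 (the f = 0.3, r = 1.5 case).
- At 30% risk: P(X ≤ 4 of 20) = 0.238 without selection, and 0.532 at risk 0.222 (the same case).

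Every illustrated bias lies below the half-width in step 1 at the same baseline risk.

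**The case against.** There is a fair case for leaving the text alone.

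- **The two bands may be deliberate.** The top-20% wording sits under Phase 1 and describes a query for 5 patients, while 4.2.1 is the formal list. The bands are nested, so every top-20% patient also meets the top-50% rule. This is plausible and it reduces the size. It does not remove the problem, because nothing states it and 4.6 does not say how controls should mirror the narrower intake.
- **The comparison is exploratory.** Section 4.6 is framed around process measures, sets no test, and the protocol looks ahead to a randomised trial. This stands and limits the severity. But readmission metrics are explicitly compared.
- **No historical control can meet a consent criterion.** True. It is a reason to say so in 4.6, not to promise identical criteria.
- **Matching or adjustment may be in an analysis plan that is not shown.** Accepted. Its absence is not part of this point.

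A reader might go further and infer that selection favours the device, or that a 10-point distortion is to be expected. The documents support neither. Nothing in them shows that decliners are at higher risk, and step 3 of the working shows the sign changing with that assumption. The 10-point figure needs all 20 patients to come from the Phase 1 query, percentiles taken within heart failure, AUC 0.70 and 30% baseline risk. Section 4.2.1 reads more naturally as system-wide percentiles. Nor do the documents say that a device effect will be claimed from 4.6.

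**Conclusion.** The point holds as an inconsistency in what the protocol states. The control definition cannot be carried out as written, and it does not identify a single criteria set. Following the text could place enrolled patients and controls in different risk bands, with only the enrolled group selected on agreement and clinical judgement.

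The net bias is unknown in size and direction. The band mismatch raises enrolled risk by about 1 to 3 points if confined to the Phase 1 patients, and by up to about 10 under the least favourable assumptions. Consent selection could offset it or add to it. These figures rest on assumed AUC, overlap, consent share and relative risk; only the 15-30% rate and the patient numbers come from the protocol. Since sampling error at 20 patients exceeds each illustrated bias, the practical harm is misinterpretation of an exploratory contrast. The text should be corrected, but the flaw does not undermine the study.

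**What to change.** 1. Reconcile the CAPE threshold and the cardiomems rule between 2.2 and 4.2.1, and apply the one resulting set to enrolled patients and controls. If a phase-specific rule is intended, say so and state how controls follow it.
2. In 4.6, list which 4.2.1 criteria are applied to charts, which are approximated and by what chart evidence, and which cannot be applied. Cover agreement to procedures, the investigator-opinion exclusion, the attending's suitability judgement in 2.2 and the monitoring-nurse criterion.
3. Where CAPE scores are available for the historical patients, restrict or match controls to the enrolled patients' CAPE range. The protocol does not say that scores exist for the full 36 months, so availability must be checked first.
4. State in 4.6 that the readmission contrast is descriptive and is not evidence of a device effect.

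The cost is wording in three sections, slight extra analysis work, some controls lost to restriction or matching, and a more modest conclusion. Selection on willingness to take part will remain beyond what CAPE captures and should be named as a limitation.

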4.7 Provisions to Protect the Privacy Interests of Participants

All study information will be stored on NorthShore University HealthSystem password-protected, encrypted computers and servers that are password protected. All of these will be stored in locked rooms and will not be accessible to those outside the study team

Patients will be given a unique study record number that is not their medical record number. This unique record number will be given to physIQ for entering into their portal. No identifying information will be provided to physIQ. The key that identifies the unique study record number to the patient MRN will only be kept by the study team and by the NorthShore teams that operationalize the study (CAPE navigators, monitoring nurse and the clinical care team).

In order to protect participant privacy, the research coordinator's phone number and office address will be registered on the physIQ pinpointIQ portal for each participant. PhysIQ's technical support team will contact the research coordinator with the subject ID to inform the research team of noncompliance use of device. The research coordinator will call participant to review device usage instruction and provide technical assistance as needed.

No PHI will be provided to physIQ and other study team members outside of NorthShore. The study team will collect patient name, MRN, date of birth, phone number for the purpose of conducting the study. All patient information will be aggregated during study analysis and no identifiers will be provided in the analysis.

Upon study completion all study data will be destroyed, and verification will be provided to data governance.

During informed consent and enrollment, the study coordinator will make sure that patients are alone or in a room with family members that the patient agrees to participate in decision making around the study. The door will be closed, and any study-related information will be paused when other staff or visitors enter the room. We will allocate 1 hour for consent, and if required, we can extend the amount of time to make sure that the patient has all their questions answered and privacy maintained.

4.8 Compensation and Economic Burden to Patients and Providers

There is no economic burden to patients who choose to participate in this study for the devices and remote monitoring. Participants will be responsible for all routine care if incurred, including home health, counseling by nurses and care providers, office visits, diagnostic tests and procedures, ER visits, and hospitalizations. If a participant is at risk of hospital readmission or has worsening conditions that require medical attention during the study period, in that case, participants will be responsible for all standard of care payments incurred during their escalation process.

Patients enrolled in the first patient group from CHF cohorts who complete all interviews with the study team will be provided a gift card as compensation for their time and participation.

There is no economic burden to care team members who choose to participate in the interview other than time spent answering questions to evaluate the process and wearable solution. We will provide a gift card to the providers as compensation for their time and participation.

DATA MANAGEMENT

5.1 Data Security

Survey data will be recorded and managed using REDCap. REDCap will contain only a subject ID, assigned by the research coordinator. The PI, research coordinator and data scientist will maintain the only linking document between study ID and patient name. It will be password protected and stored on Northshore University HealthSystem's secure internal server. During the study period, the operational team will also receive access to the linking information to identify which patients are in the pinpointIQ portal. Other study team members will not have access to the key.

PhysIQ's solution, including wearable devices, mobile device and cloud platform on Microsoft Azure was evaluated and approved by data security (HIT) as part of a prioritized active project. No PHI will be uploaded to the physIQ platform. The vital and alert data will be transferred back to NorthShore for storage using an sFTP. PhysIQ's telemonitoring platform will be used for the study procedure. PhysIQ will not receive any protected health information.

PhysIQ operates in line with both HIPAA and GDPR. Neither HIPAA nor GDPR support an external authority that can formally attest to compliance, but physIQ does operate and measure its internal security and privacy program against both frameworks and is operating in line with each.

There are three (3) core components of the physIQ product; 1) a 3rd party disposable patch worn by the patient, 2) a physIQ supplied mobile phone running as a data hub, and 3) a web browser-based clinical portal for viewing analytics and raw data. The data flow within these basic components is secure at all time. No sensitive and/or protected data resides in the physIQ offices nor on the corporate network.

The sensor patch collects physiological data (not considered PHI) and through a 128-bit encrypted Bluetooth offload, transmits that data to an Android-based, dedicated lockdown (kiosk) mobile phone, which is validated and approved to interface and collect patient data. The device is provided by physIQ; this is not a bring-your-own-device (BYOD) system. In kiosk mode this device runs only the physIQ mobile application with no ability to make calls, SMS text, nor internet browsing. All Bluetooth offloaded physiological data is stored in Android's encrypted memory. Furthermore, all data is deidentified; there is no PHI on the mobile device. The phone is assigned a "node ID" in the cloud platform which functions as the alias and link to the specific phone. Uploads are made to the cloud with the node ID credentials. The mobile phone then uploads the data through cellular connection to physIQ's Google Cloud Services (GCS) cloud platform.

The physIQ cloud architecture includes service relationships with certified partners. The production (VPC) stack is in GCS, with the back-up snapshot in Amazon Web Services (AWS). The physIQ platform is an isolated GCS network inside which servers communicate with limited pinholes to the outside world. Port 443 is the "front door" and uses TLS encryption for all traffic. All data exchange is sanctioned and handled by the API. physIQ's product is entirely API-enabled. Mobile phone (node) uploads of data and Clinical Portal browser sessions are both API calls. There are also two (2) VPN "back doors" for occasional maintenance of the VPC and for the read-only requests from AWS for back-ups.

Other cloud security measures include; role-based-access-controls (RBAC) for all URL routes in the API and inside the product, all data-at-rest in GCS and AWS is encrypted by default schema, all patients in the

system are known by GUIDs and identity data is stored separately from medical data, and all servers (VMs) are instances of a security-hardened image

Carnegie Mellon University (CMU) is a collaborating site and will have access to de-identified and date shifted patient and healthcare provider information. No HIPAA identifiers will be included in the data shared with CMU. Collaborators at CMU will be involved in developing and evaluating the 30-day readmission prediction model. Deidentified and date shifted data will be transferred to CMU over a Secure Sockets Layer (SSL) using a HIPAA compliant File Transfer Protocol (FTP). Data will be stored at NorthShore and at CMU on password-protected, encrypted computers. All research team members and graduate and doctoral students working with the data will complete Human Subjects Research certification. After completion of this project, all data at both NorthShore and CMU will be destroyed.

